### **9.3. Safety Analysis**

The safety data will be summarized in accordance with Pfizer Data Standards. All subjects who receive investigational product (safety population) will be included in the safety analyses. All safety data will be summarized descriptively through appropriate data tabulations, descriptive statistics, categorical summaries, and graphical presentations. Safety endpoints for the study include:

- Treatment-emergent AEs and SAEs;
- Withdrawals from active treatment due to AEs;
- Serious infections, defined as any infection (viral, bacterial, and fungal) requiring hospitalization or parenteral antimicrobials or meets other criteria that require it to be classified as a serious adverse event, will be summarized;
- Safety laboratory tests (eg, hematology [including coagulation panel], chemistry and lipid profiles);
- Vital signs;
- ECG parameters if applicable.

Change from baseline on laboratory data and vital signs will be additionally summarized.

Subject listings will also be produced for these safety endpoints.

All safety data will be summarized separately for each of the following key subgroups:

- Subjects who have received at least one dose of study drug during the open label run-in period. These subjects would have a cumulative exposure to 200 mg QD PF-04965842 of up to 12 weeks;
- Subjects who have been randomized and have received at least one dose of randomized study treatment. Summaries of safety data will be reported for these subjects by randomized treatment regimen;
- Subjects who meet loss of response criteria during the randomized, double-blind period and receive at least one dose of rescue treatment. Summaries of safety data will be reported for these subjects by randomized treatment regimen.

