3.5. Safety Endpoints

Safety will be assessed by the spontaneous reporting of AEs, physical examinations, and clinical laboratory results in all subjects who receive at least one dose of the investigational product. Unscheduled safety assessments may be performed at any time during the study to assess any perceived safety concerns. Endpoints will be assessed as,

- Treatment-emergent adverse events.
- Treatment-emergent SAEs and AEs leading to discontinuation.
- Clinical abnormalities and change from baseline in selected clinical laboratory values, ECG measurements, and vital signs.

The safety endpoints will be defined in accordance with Clinical Data Interchange Standards Consortium (CDISC) and Pfizer Standards (CaPS).

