3.5.1. Adverse Events

An adverse event is considered TEAE to a given treatment if the event started during the effective duration of treatment. All events that start on or after the first dosing day, but before or on the last dosing day plus the lag time (28 days) will be flagged as TEAEs. The algorithm will not consider any events that started prior to the first dose date.

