6. ANALYSES AND SUMMARIES

Treatment comparisons will only be displayed for the FAS-RA analysis set where it is relevant. Pairwise comparisons will be reported among the treatment groups. No treatment comparisons are relevant for the FAS-OL and FAS-RE analysis sets. Similarly, safety data displays will be by treatment group only for SAF-RA and not for SAF-OL or SAF-RE.

A summary of analyses for clinical efficacy endpoints is provided in [Appendix 1](#). Visit windows to be used for all efficacy analyses and some relevant safety analyses are detailed in [Appendix 2](#).

Efficacy and PRO data collected at the Week 16/Week 56 follow-up visits or at the Rescue Visit Week 16 follow-up visit will be displayed in listings only, and will not be part of any analyses, unless specifically noted otherwise.

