6.7. Safety Summaries and Analyses

Safety analysis will be based on the SAF analysis sets (see [Section 4.3](#)). The SAF-OL analysis set will be used to summarize the safety experience for all subjects during the first 12 weeks of open label treatment with PF-04965842 200 mg QD using the Study Baseline (see [Section 3.4](#)). The SAF-RA analysis set will be used to summarize the safety experience for all randomized subjects using the Randomization Baseline. Subjects who report a protocol-defined flare and get rescue treatment will be censored at the day before the first day of rescue in this analysis. All subjects will be classified according to the actual treatment regimen they received. The SAF-RE analysis set will be used to summarize the safety experience for the subjects who receive rescue treatment using the Rescue Baseline. Study Baseline will be used for all displays of results meeting lab abnormality criteria, throughout the subject's study experience.

All clinical AEs, SAEs, treatment-emergent signs and symptoms (TEAEs), withdrawal due to AEs, ECGs, vital signs and safety laboratory data will be summarized to evaluate the safety of subjects.

Safety data will be presented in tabular and/or graphical format and summarized descriptively, where appropriate. All safety endpoints will be listed and summarized in accordance with Pfizer Standards. Categorical outcomes (eg, AEs) will be summarized by subject counts and percentage. Continuous outcome (eg, blood pressure, pulse rate, etc.) will be summarized using N, mean, median, standard deviation, etc. Change from baseline in laboratory data, ECGs and vital signs will also be summarized. Subject listings will be produced for these safety endpoints accordingly. Separate summaries will be displayed for adjudicated data on cardiovascular (CV), malignancy, opportunistic infection, histopathologic and hepatic events.

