6.7.1. Adverse Events

The safety data will be summarized in accordance with Pfizer Data Standards. All safety data will be summarized descriptively through appropriate data tabulations, descriptive statistics and categorical summaries. Safety endpoints for the study include:

- Treatment-emergent AEs and SAEs;
- Withdrawals from active treatment due to AEs;
- Serious infections, defined as any infection (viral, bacterial, and fungal) requiring hospitalization or parenteral antimicrobials.

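### The only by-arm safety display stops follow-up at rescue but names only n (%) for adverse events, so at equal hazard the arm that holds its response longer can look worse

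*SAP*

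**What the plan says.** SAP 6 limits by-arm safety output to the randomized set: "safety data displays will be by treatment group only for SAF-RA and not for SAF-OL or SAF-RE". SAP 6.7 sets the end of follow-up in that set: "Subjects who report a protocol-defined flare and get rescue treatment will be censored at the day before the first day of rescue". For AEs it names one measure: "Categorical outcomes (eg, AEs) will be summarized by subject counts and percentage". SAP 6.7.1 adds only descriptive tabulations and categorical summaries.

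The SAP also defers to outside standards, which are not among the documents:
- SAP 3.5: "The safety endpoints will be defined in accordance with Clinical Data Interchange Standards Consortium (CDISC) and Pfizer Standards (CaPS"
- SAP 6.7: "All safety endpoints will be listed and summarized in accordance with Pfizer Standards"
- SAP 6.7.1: "The safety data will be summarized in accordance with Pfizer Data Standards"

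Two other displays show that follow-up differs between arms: total days of dosing (SAP 6.6.3) and time-to-flare curves with numbers at risk (SAP 5.2.4). Neither is tied to AE counts. The time origins and accrual periods in SAP 5.2.4 are set only for the FAS sets.

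For subjects who enter rescue, Protocol 9.3 states: "Summaries of safety data will be reported for these subjects by randomized treatment regimen". SAP 6 does not carry this forward.

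**The concern.** Safety follow-up in SAF-RA is ended by the efficacy outcome. A subject who flares leaves the display and a subject who keeps responding stays in it for up to 40 weeks. If the drug works, placebo subjects are watched for less time, and the arms are then compared by a percentage that takes no account of time at risk.

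This is the only by-arm view of TEAEs, SAEs, discontinuations for AEs, serious infections and adjudicated events. For non-AD events with persisting risk, a reader of n (%) cannot separate a higher hazard on active drug from a longer response. With the rescue-period display by randomized regimen dropped, no second by-arm table offsets this.

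**Working it through.** **Inputs from the documents.** Blinded period 40 weeks; 200 per arm; planned ratio of median time to flare 1.5; two-sided 5%; 94% power (SAP 2.2). Flare is assessed at Weeks 16, 28, 40 and 52, that is 4, 16, 28 and 40 weeks after randomization (Schedule of Activities), and at unscheduled visits (Protocol 5.2). Any clinically significant AD worsening counts as an AE (Protocol 8.1).

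**Assumed inputs.** The documents give no placebo median, dropout rate or AE rate. The base case is exponential flare, placebo median 16 weeks (active 24), no dropout, and the same AE hazard *a* in both arms, with a 52-week year.

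**The plan's power figure.** Flare hazards are L = ln2/16 = 0.0433 and ln2/24 = 0.0289 per week. Expected flares by 40 weeks: 200 × (0.823 + 0.685) = 301.6. Power = Φ(ln1.5 × √(301.6/4) − 1.96) = 0.941. A 16-week median is therefore consistent with the planned 94%, though not established by it.

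**Formulas.**
- Flare detected at once: mean follow-up = (1 − e^(−40L))/L; crude AE proportion = a/(a+L) × (1 − e^(−40(a+L))).
- Scheduled visits only: sum over v = 4, 16, 28, 40 of Pr(detected or ended at v) × (1 − e^(−av)).

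For visits only with a = 1/52, the terms 1 − e^(−av) are 0.074, 0.265, 0.416 and 0.537. The visit probabilities are 0.159, 0.341, 0.203 and 0.297 on placebo, and 0.109, 0.261, 0.185 and 0.445 on active. The sums are 34.6% and 39.3%.

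**Results, placebo vs active, true hazards equal.**

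| | At once | Visits only |
|---|---|---|
| Mean follow-up, weeks | 19.0 vs 23.7 | 23.7 vs 27.6 |
| AE %, 1 per patient-year | 28.2 vs 34.1 | 34.6 vs 39.3 |
| AE %, 0.5 per patient-year | 16.0 vs 19.6 | 19.7 vs 22.7 |
| Subjects of 200, 0.05 per patient-year | 3.6 vs 4.5 | 4.5 vs 5.2 |
| AE %, 1 per patient-year, 20% dropout by 40 weeks in both arms | 26.4 vs 31.6 | 32.2 vs 36.3 |

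At 1 per patient-year the gaps are 5.9 and 4.7 points. The standard error of a difference with 200 per arm is √(0.282×0.718/200 + 0.341×0.659/200) = 4.6 points at once, and 4.8 points for visits only by the same formula. The gaps are thus about 1.3 and 1.0 standard errors. Placebo medians of 12 to 24 weeks give gaps of 6.2 to 5.1 points (at once) and 5.1 to 3.9 (visits only).

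**Where the effect fades or turns.**
- *Early onset.* With a 50% risk confined to the first 4 weeks (hazard ln2/4), crude figures are 46.4 vs 47.5% (at once) and 50.0 vs 50.0% (visits only). Here the exposure-adjusted rate misleads: 233 vs 194 per 100 patient-years (ratio 0.83) and 204 vs 177 (ratio 0.87).
- *Total AEs.* If a share q of flares is also recorded as AEs, add q × L/(a+L) × (1 − e^(−40(a+L))) for detection at once, or q × the sum of Pr(flare detected at v) × e^(−av) for visits only. For q = 25%, 50% and 100%, detection at once gives 44.1 vs 47.0, 60.0 vs 59.8 and 91.8 vs 85.4%. Visits only gives 48.9 vs 50.8, 63.2 vs 62.4 and 91.8 vs 85.4%.

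**The alternative measure.** For non-AD AEs at 1 per patient-year, 1 minus Kaplan-Meier at 40 weeks targets 1 − e^(−40/52) = 53.7% in both arms under either detection pattern. This rests on AE times being independent of flare, which the calculation assumes.

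**The case against.** **The reporting standards may already require rates.** They cannot be seen, so what is shown is silence in the SAP rather than a missing analysis. This stands as a limit, and naming the display in SAP 6.7 would settle it.

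**The affected territory is narrow.** Rare and early-onset events are barely touched, total AEs may show no gap, the clearest illustrated case is about one standard error, and no decision rule uses n (%). Most event classes of interest are plausibly low-rate. All of this is accepted and is why the point ranks as an improvement to consider.

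**Kaplan-Meier assumes independence that some target events may lack.** Protocol Appendix 2 lists a tendency to cutaneous infection as a feature of AD, and Protocol 9.6 includes eczema herpeticum among adjudicated events. Take a gamma frailty of variance v shared by flare and AE, with base-case hazards and detection at once. Then 1 minus Kaplan-Meier tends to 1 − (1+40v(a+L))^(−a/(v(a+L))), the crude proportion is a/(a+L) × (1 − (1+40v(a+L))^(−1/v)), and the true risk is 1 − (1+40va)^(−1/v). For v = 0.5, Kaplan-Meier gives 39.3 vs 41.7% and crude 24.7 vs 29.6%, against a true 47.8%. For v = 1 the figures are 32.0 vs 34.9% and 22.0 vs 26.3%, against 43.5%. Kaplan-Meier is then biased low with a residual arm gap, but it is closer to the truth than the crude figure and its gap is smaller.

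**Unequal dropout could shrink the gap.** Adding dropout hazard d to a+L, with d = −ln(0.9)/40 on placebo and −ln(0.7)/40 or −ln(0.6)/40 on active, gives 27.3 vs 30.3% or 28.8%. The gap falls to 3.0 or 1.5 points without reversing.

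**Conclusion.** The point holds. The SAP text commits to no AE measure that accounts for time at risk, in the one safety set where arms are compared and where the primary endpoint ends follow-up. For non-AD events with persisting risk, crude percentages run higher in the longer-responding arm at equal hazard. Under the stated assumptions the gap is about 5 to 6 points at 1 event per patient-year and 3.0 to 3.6 points at 0.5.

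The direction requires persisting risk and longer follow-up on active drug. The size depends on an assumed placebo median, detection pattern and AE rate. It does not apply to early-onset events, amounts to less than one subject per arm for rare events, and may cancel or reverse for total AEs. It concerns how safety tables will be read and does not touch the efficacy conclusion. Confidence is moderate because the reporting standards are unseen.

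**What to change.** In SAP 6.7, for SAF-RA by arm:

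- Beside n (%), add 1 minus Kaplan-Meier for time to first event, censored at rescue, with 95% CI. Cover TEAEs, SAEs, AEs leading to discontinuation, serious infections and adjudicated events, each excluding AD worsening. Fix the list of excluded terms before unblinding.
- Give exposure-adjusted rates per 100 patient-years with 95% CI as a companion.
- Keep n (%) for AD worsening and total AEs.
- State that the day-before-rescue cut overrides the general TEAE window in SAP 3.5.1 ("before or on the last dosing day plus the lag time (28 days) will be flagged as TEAEs"), and use the same cut for time at risk. This is clarification only.
- If the sponsor's standards already require such a display, name it here instead.

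Separately, reconcile Protocol 9.3 and SAP 6 on rescue-period safety by randomized regimen.

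The cost is SAP wording, a term list and a few tables, with no new data. Two cautions belong in the text. Exposure-adjusted rates assume a roughly constant hazard and mislead for early-onset events. Kaplan-Meier assumes non-AD risk is unrelated to flare, and its late estimates will be imprecise: in the base case only 200 × (1 − 0.823) ≈ 35 placebo subjects are flare-free at 40 weeks.

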6.7.1. Adverse Events

The safety data will be summarized in accordance with Pfizer Data Standards. All safety data will be summarized descriptively through appropriate data tabulations, descriptive statistics and categorical summaries. Safety endpoints for the study include:

- Treatment-emergent AEs and SAEs;
- Withdrawals from active treatment due to AEs;
- Serious infections, defined as any infection (viral, bacterial, and fungal) requiring hospitalization or parenteral antimicrobials.

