### **8.2.3. Serious Adverse Events**

A serious adverse event is any untoward medical occurrence at any dose that:

- Results in death;
- Is life-threatening (immediate risk of death);
- Requires inpatient hospitalization or prolongation of existing hospitalization;
- Results in persistent or significant disability/incapacity (substantial disruption of the ability to conduct normal life functions);
- Results in congenital anomaly/birth defect.

Or that is considered to be:

- An important medical event.

Medical and scientific judgment is exercised in determining whether an event is an important medical event. An important medical event may not be immediately life-threatening and/or result in death or hospitalization. However, if it is determined that the event may jeopardize the subject or may require intervention to prevent one of the other AE outcomes, the important medical event should be reported as serious.

Examples of such events are intensive treatment in an emergency room or at home for allergic bronchospasm; blood dyscrasias or convulsions that do not result in hospitalization; or development of drug dependency or drug abuse.

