### **Discontinuation Criteria**

Subjects must be permanently discontinued from treatment if they meet any of the following criteria at any point in the study:

- Marked prolongation of the Fridericia-corrected QT (QTcF) interval to  $>500$  ms or  $>60$  ms change from screening ECG.
- Serious infection (see definition for Serious Adverse Events in [Section 8.2.3](#)).

- Any bleeding event thought to be associated with a platelet count reduction per the judgement of the investigator (or, if necessary/desired, following discussion with sponsor).
- Other adverse event, per judgment of the investigator, requiring discontinuation from treatment (or, if necessary/desired, following discussion with sponsor).
- Any adverse event or laboratory abnormality, that per the investigator's judgement requires temporary interruption to dosing of investigational product for >28 days.

NOTE: any initial lab value below must be retested, within 48 hours.

- Two sequential platelet counts  $<50,000/\text{mm}^3$ . If the subject has a platelet count  $<25,000/\text{mm}^3$ , investigational product should be temporarily withheld pending the confirmatory retest.
- Two sequential neutrophil counts  $<500/\text{mm}^3$ .
- Two sequential lymphocyte counts  $<500/\text{mm}^3$ .
- Two sequential hemoglobin assessments  $<8.0 \text{ g/dL}$  or  $\leq 30\%$  from baseline value.

Any of the following:

- Two sequential AST or ALT elevations  $>3$  times the upper limit of normal with at least one total bilirubin value  $>2$  times the upper limit of normal.
- Two sequential AST or ALT elevations  $>3$  times the upper limit of normal with an abnormal INR.
- Two sequential AST or ALT elevations  $>3$  times the upper limit of normal accompanied by symptoms consistent with hepatic injury.
- Two sequential AST or ALT elevations  $>5$  times the upper limit of normal, regardless of total bilirubin or accompanying symptoms.

**Note: Any of the above findings should prompt review of “The Potential Cases of Drug-Induced Liver Injury”, [Section 8.4.1](#) for which additional investigations must be conducted.**

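### The serious-infection definition in SAP 6.7.1 omits the protocol's third limb, so an infection that is serious only under the other SAE criteria is left out of that summary

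*SAP*

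**What the plan says.** SAP 6.7.1 names three kinds of safety summary: treatment-emergent AEs and SAEs, withdrawals from active treatment due to AEs, and "Serious infections, defined as any infection (viral, bacterial, and fungal) requiring hospitalization or parenteral antimicrobials". The definition has two limbs.

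Protocol 9.3 (Safety Analysis) has the same item and the same opening words, but continues "or meets other criteria that require it to be classified as a serious adverse event, will be summarized". That makes three limbs.

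The protocol's SAE criteria are in 8.2.3. Besides hospitalization they include "Results in death", "Is life-threatening (immediate risk of death", "Results in persistent or significant disability/incapacity", and important medical events. On the last of these 8.2.3 says "An important medical event may not be immediately life-threatening and/or result in death or hospitalization".

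The discontinuation criteria in protocol Appendix 4 also use the term, by reference to the SAE section: "Serious infection (see definition for Serious Adverse Events in" 8.2.3.

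No other SAP section restores the third limb. The change table in SAP section 1 does not itemise the narrower wording. Its only related entry is a general one about minor changes for clarity and alignment with the protocol.

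**The concern.** Protocol 1.5 names serious and opportunistic infection among the potential risks of treatment, so readers will look at the serious-infection count directly. The SAP reproduces the protocol's sentence and then drops the limb that ties it to seriousness as such. It gives no reason, and the change does not look deliberate.

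What is at stake is whether the reported number means what the protocol says it means. A programmer following SAP 6.7.1 exactly would leave an infection out of the serious-infection summary although it had been reported and handled as an SAE throughout the trial. The departure runs one way, towards fewer events. It would affect the open-label, randomized and rescue safety sets alike, since SAP 6.7 uses all three.

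**Working it through.** No plan figure needs reproducing; the check compares definitions.

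**Inputs.** Among viral, bacterial and fungal infections (the restriction is in both documents), let

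- H = those requiring hospitalization,
- P = those requiring parenteral antimicrobials,
- S = those classified as an SAE under protocol 8.2.3.

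**Definitions.**

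- Protocol 9.3: H or P or S.
- SAP 6.7.1: H or P.
- Difference, protocol minus SAP: infections in S but in neither H nor P.

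The SAP set is contained in the protocol set, so the difference is zero or positive and cannot be negative. The same holds when subjects rather than events are counted.

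**Is the omitted limb empty by construction?** No. Death, life threat, disability and important medical event are separate criteria in 8.2.3, and none requires admission or a parenteral drug. Protocol 8.2.4 adds that attending an emergency room is not necessarily a hospitalization. Protocol 8.1 lets the sponsor reclassify a non-serious AE as serious. Each is a route into S that bypasses H and P.

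**Cases side by side.**

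| Infection | Protocol 9.3 | SAP 6.7.1 | Appendix 4 term |
|---|---|---|---|
| Admitted to hospital | yes | yes | yes |
| Parenteral antimicrobial, not admitted, not an SAE | yes | yes | no |
| SAE by death, life threat, disability or medical importance; no admission, no parenteral drug | yes | **no** | yes |
| Oral treatment, no SAE criterion met | no | no | no |
| SAE, but not viral, bacterial or fungal | no | no | yes |

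The third row is the defect. The second and last rows show that the Appendix 4 term and the analysis definition differ in both directions even within the protocol, so Appendix 4 is context here and not the standard for judging the SAP.

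**Where a third-row case is still reported.** It is an SAE, so if treatment-emergent it is in the AE/SAE summary of SAP 6.7.1. If treatment ended because of it, it is also in the withdrawals summary. SAP 6.7 adds subject listings and a separate display of adjudicated opportunistic infections, which covers only some infections.

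**Can the protocol count be rebuilt from those tables?** Not reliably. It is the union of infection SAEs and parenterally treated infections. The two groups overlap, so summary counts cannot simply be added; a reader would need subject-level data.

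**Size.** The number omitted equals the number of third-row cases. The documents give neither an expected infection rate nor the share of infection SAEs that avoid both admission and parenteral therapy. No estimate follows from them, and zero is possible.

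**The case against.** The strongest reply is that little is lost. Every omitted infection is an SAE and, if treatment-emergent, stays visible in the SAE summary. Serious infection is not among the endpoints in protocol Table 1, SAP Table 2 or SAP 3.5. Safety is descriptive, so no test or decision rule is touched. One definition applies to all arms. SAP section 2 allows the SAP to modify the protocol, and only major changes to the primary endpoint or its analysis require an amendment.

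All of that stands, and it limits the point to one descriptive summary. It does not remove it. Permission to modify does not explain a narrowing that is neither stated nor justified, and the SAE table does not show the protocol-defined count.

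Stronger readings are tempting, and the documents do not support them:

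- A reader might infer that these infections disappear from the safety report. They do not.
- A reader might expect a visible mismatch between subjects discontinued for serious infection and subjects reported as having one. Neither document plans a count of discontinuations for serious infection; the SAP plans withdrawals due to AEs and general disposition.
- A reader might expect the restored clause to bring every infection that ended treatment under Appendix 4 into the table. That cannot be guaranteed, because both analysis definitions are limited to viral, bacterial and fungal infections and Appendix 4 is not.
- A reader might put a number on the shortfall from assumed rates. Nothing in the documents anchors such rates.

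**Conclusion.** The definition in SAP 6.7.1 is narrower than that in protocol 9.3, without explanation. Followed exactly, it gives a serious-infection count equal to or lower than the protocol-defined count for a risk that the protocol names. The textual difference is certain and so is its direction. The size cannot be estimated from the documents and may be zero. No bias in a comparison between arms is shown, and no amendment rule is broken.

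The conclusion assumes that the table is programmed from the SAP wording. SAP 6.7 also refers to the sponsor's reporting standards, which are not part of the documents. If those carry the wider definition, the table may come out right, but the SAP sentence would still misdescribe it.

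**What to change.** In SAP 6.7.1, complete the definition with the protocol 9.3 clause, so that an infection also counts when it meets any other SAE criterion. Apply it in the serious-infection summaries for SAF-OL, SAF-RA and SAF-RE, taking seriousness from the SAE record, including any sponsor reclassification under protocol 8.1. Note the correction in the SAP's change table.

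The cost is one clause and a small programming change. No new data are needed, because protocol 8.1 already requires every SAE to be recorded on the CRF. The downside is that the reported count may be slightly less favourable. If the sponsor does intend the narrower definition, the SAP should say so and give the reason, and the table should be labelled accordingly. The treatment-discontinuation rule in Appendix 4 is not affected.
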